8.8 Safety Analyses

8.8.1 Adverse Events

All AEs will be classified by system organ class and preferred term using the Medical Dictionary for Regulatory Activities (MedDRA). TEAEs will be tabulated in a manner which provides information about the incidence of TEAEs for the entire treatment period as well as by time period in order to understand the evolution of TEAEs over time. Thus, in addition to the TEAE analysis over the entire 12-month treatment time, results will be presented for the following periods: 0 to 4 weeks, > 4 to 12 weeks, > 12 to 28 weeks, > 28 weeks to 36 weeks, > 36 to end of treatment, and end of treatment to end of the study (including by weekly periods from end of treatment to end of study). For incidence reporting, if a subject reported more than one TEAE that was coded to the same system organ class or preferred term, the subject will be counted only once for that specific system organ class or preferred term. An overview of AEs, which includes subject incidence of AEs, TEAEs, treatment-related TEAEs, TEAEs by severity, SAEs, deaths, and AEs leading to discontinuation, will be presented.

All information pertaining to AEs noted during the study will be listed by subject and will include a verbatim description of the event as reported by the investigator, as well as the preferred term, system organ class, start date, end date (if ended), seriousness, severity, action taken regarding the study drug, outcome, and relationship to the study drug. In addition, a listing of subjects who prematurely discontinue from the study due to AEs will be provided.

SAEs will be listed and summarized in a similar manner to AEs.

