#### 2. INTRODUCTION

The MTI-107 study described herein is an open-label study to assess the long-term safety of serlopitant in adults with pruritus associated with prurigo nodularis (PN), atopic dermatitis (AD), or psoriasis.

Subjects enrolled in MTI-107 may have or may not have participated in previous Menlo Therapeutics Inc. studies. Previous study participation includes studies in PN (MTI-105, MTI-106, TCP-102), in AD (MTI-103) and in psoriasis (MTI-109).

The MTI-107 study has been terminated early by Sponsor. The Statistical Analysis Plan has been updated to facilitate an abbreviated clinical study report.

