#### 3. STUDY OBJECTIVES

The primary objective of this study is to assess the long-term safety of serlopitant in adults with pruritus associated with PN, AD, or psoriasis.

The secondary objectives of this study are to assess the change in severity of pruritus in subjects with PN, AD, or psoriasis using the worst-itch numeric rating scale (WI-NRS); to assess the change in severity and extent of PN using the Investigator's Global Assessment of PN Stage

Statistical Analysis Plan for Menlo Therapeutics Inc. Protocol Number: MTI-107

(IGA PN-S), for those subjects with PN; and to assess whether serlopitant produces physical dependence.

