#### 4. STUDY DESIGN

# 4.1 Overall Study Design

This is a multicenter, open-label study to assess the long-term safety of serlopitant in adults with pruritus associated with PN, AD, or psoriasis. Eligible subjects who have completed selected studies of serlopitant may be given the opportunity, at the Investigator's discretion, to consent to and participate in this open-label study, regardless of their treatment allocation in prior studies. If deemed necessary by Menlo Therapeutics to meet enrollment objectives, eligible subjects who have not participated in a prior serlopitant study may also be enrolled in study MTI-107. Approximately 120 study sites may enroll subjects in this long-term safety study.

This study will consist of two periods, for a total study period of 57 weeks:

• Treatment period: 52 weeks

• Post-drug observation period: 5 weeks

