# **6.8** Safety Evaluation

# **6.8.1** Extent of Exposure

The extent of exposure to study drug will be summarized by days with exposure and total number of tablets used. Subjects will be considered having 6-Month exposure if the date of first dose – date of last dose + 1 is greater than or equal to 182 days. Subjects will be considered having 1-Year exposure if date of first dose – date of last dose + 1 is greater than or equal to 358 days, considering the allowable -7 day window for the Week 52 visit.

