#### 6.8.2 Adverse Events

All AEs will be classified by system organ class and preferred term using the MedDRA. TEAEs will be tabulated in a manner which provides information about the incidence of TEAEs for the entire study. For incidence reporting, if a subject reported more than one TEAE that was coded to the same system organ class or preferred term, the subject will be counted only once for that

specific system organ class or preferred term. An overview of AEs, which includes subject incidence of AEs, TEAEs, treatment-related TEAEs, TEAEs by severity, SAEs, deaths, and AEs leading to discontinuation of study drug, will be presented.

All information pertaining to AEs noted during the study will be listed by subject and will include a verbatim description of the event as reported by the investigator, as well as the preferred term, system organ class, start date, end date (if ended), seriousness, severity, action taken regarding the study drug, outcome, and relationship to the study drug. In addition, a listing of subjects who prematurely discontinued study drug due to AEs will be provided.

SAEs will be listed and summarized in a similar manner to AEs.

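### After early termination the SAP reports adverse events as whole-study percentages with no time base, so one-year incidence cannot be read from them and will tend to look too low where treatment was cut short

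*SAP*

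**What the plan says.** SAP 3 states the aim: "The primary objective of this study is to assess the long-term safety of serlopitant in adults with pruritus associated with PN, AD, or psoriasis". SAP 4.1 sets the design ("Treatment period: 52 weeks", followed by a five-week post-drug period). SAP 2 then reports that "The MTI-107 study has been terminated early by Sponsor" and that the plan was revised for a shortened report.

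For adverse events, SAP 6.8.2 says "TEAEs will be tabulated in a manner which provides information about the incidence of TEAEs for the entire study". When a subject has several events under one system organ class or preferred term, "the subject will be counted only once for that" class or term. The system organ class and preferred term tables, for all and for serious TEAEs, show n (%) of the safety population. The overall table (14.3.1.1.1) also shows total numbers of TEAEs, related TEAEs, serious TEAEs and related serious TEAEs. The note to Table 14.3.1.3.1.1 counts any event starting after the first dose and sets no end to the window.

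Exposure is handled apart from events: "The extent of exposure to study drug will be summarized by days with exposure and total number of tablets used", with counts of subjects reaching at least 182 and at least 358 days (SAP 6.8.1, Table 14.3.0.1).

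Protocol 8.8.1 planned more. Besides the full treatment period, "results will be presented for the following periods: 0 to 4 weeks, > 4 to 12 weeks, > 12 to 28 weeks", then two later on-treatment periods and a post-treatment period split by week. SAP 6.8.2 has none of these. SAP 8 names only the laboratory graphs as dropped and otherwise says in general terms that the analyses were cut down.

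**The concern.** In a 52-week single-arm study that most subjects finish, the percentage with an event is roughly a one-year risk. Once the sponsor stops the study, a subject whose treatment ends at Week 10 stays in the denominator with the same weight as a completer. The percentage then has no defined time frame. Events that accrue steadily or start late are the most affected, and these are the events a long-term safety study is meant to find.

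The by-period tables would have shown how risk changes with time on drug. Without them, no planned table ties an event to time at risk. Because the window runs past the last dose, on-drug and off-drug events are also pooled.

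**Working it through.** **No figure to reproduce.** The SAP has no sample size calculation and no inference, and it states no expected incidence. It gives no termination date, enrolment dates or exposure distribution. The inputs below marked as assumed are therefore illustrative.

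**Inputs.** Treatment lasts 52 weeks and post-drug observation 5 weeks (SAP 4.1). Assumed: true 52-week risk R = 10%; constant hazard; a share f of subjects truncated, stopping uniformly over Weeks 4 to 52; all others complete.

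**Formula.** The weekly hazard is λ = −ln(1 − R)/52 = 0.10536/52 = 0.002026. With u weeks of follow-up counted after the last dose:

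crude proportion = (1 − f) × A + f × B

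where A = 1 − exp(−λ(52 + u)), and B is the mean of 1 − exp(−λ(t + u)) for t uniform on 4 to 52.

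- On-drug time only (u = 0): A = 0.1000, B = 0.0548.
- Five follow-up weeks for everyone at the same hazard (u = 5): A = 0.1091, B = 0.0643.

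| Share truncated | On-drug only | Ratio to 10% | With 5 weeks added | Ratio to 10% |
|---|---|---|---|---|
| 25% | 8.9% | 0.89 | 9.8% | 0.98 |
| 50% | 7.7% | 0.77 | 8.7% | 0.87 |
| 75% | 6.6% | 0.66 | 7.5% | 0.75 |

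The understatement is about 11%, 23% and 34% on drug only, and about 2%, 13% and 25% with follow-up. The SAP tabulates the entire study, so the second set is closer to its window for subjects who complete follow-up. Subjects without follow-up pull the result towards the first set. For a true risk of 2%, the on-drug figures are 1.8%, 1.5% and 1.3%.

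**Where the sign turns.** For uncommon events the whole-study percentage matches the 52-week risk when mean time on drug is about 47 weeks (47 + 5 = 52). Here the mean is 52 − 24f, since truncated subjects average 28 weeks, so the break-even is f = 5/24, about 21%. With stopping spread over Weeks 0 to 52 instead and 90% completing, the ratio with follow-up is 1.04.

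**Shape of the hazard.** With a front-loaded hazard (Weibull shape 0.5), half completing, the rest stopping over Weeks 0 to 52, and on-drug time only, the ratio is 0.84. The constant hazard gives 0.75 in the same setting. Early events are understated less.

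**Check of the remedy.** Take f = 50%, on-drug time only. First events per subject are 0.0774, and person-time to first event or last dose is 0.0774/0.10536 = 0.735 years per subject. The rate is 10.5 per 100 patient-years, and 1 − exp(−0.1054) = 10.0%. The exact recovery follows from the assumed constant hazard.

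**Exposure formula.** SAP 6.8.1 and the footnote to Table 14.3.0.1 write first dose minus last dose plus 1. For 364 days on drug this gives −363 + 1 = −362, so taken literally nobody reaches either threshold. The thresholds themselves are consistent: 364 − 7 + 1 = 358 and 26 × 7 = 182.

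**The case against.** The strongest reply is that little is misstated. The SAP never calls its percentages one-year incidence; it says they cover the whole study. The study is descriptive and single-arm, and the report is deliberately short. The protocol did not plan exposure-adjusted rates either. The overall table gives event totals, and Table 14.3.0.1 gives the number of subjects and mean days. A reader can therefore form a crude overall event rate and, from the 6-month and 1-year counts, judge how far exposure was truncated. Dated by-subject listings allow more to be rebuilt.

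Most of that stands, and it limits the point to a missing time base. It does not remove it. The planned tables give no first-event rate for any system organ class, preferred term or serious event, and rebuilding rates from listings is not a planned analysis. The period tables, which the protocol did plan, were dropped without being named.

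A reader might go further and infer that time on drug was very unequal and that one-year incidence is therefore understated as a fact. The documents do not support that. They say only that the study ended early. The sponsor-decision row in Table 14.0.1.1 is one of several possible reasons for stopping treatment and carries no count.

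**Conclusion.** The point holds as a gap in reporting. The TEAE tables do not support a statement about one-year or long-term incidence, and they will tend to understate it to the extent that treatment was cut short. The size is unknown. Under the assumptions above the understatement runs from about 2% to 34% in relative terms, and it reverses slightly if nearly all subjects complete and follow-up is counted. It rests on an assumed hazard shape and stopping pattern.

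It would also be tempting to say that truncation is what spoils comparison with the earlier 6- and 8-week Phase 2 studies. That does not follow. A 52-week percentage would not compare with an 8-week one under full follow-up either, and the 6-week study is not among the prior studies listed in SAP 2.

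This is a recommended and inexpensive improvement to how the primary objective is reported.

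**What to change.** - **SAP 6.8.2:** keep n (%). Add patient-years at risk and subjects with a first event per 100 patient-years to Tables 14.3.1.1.1, 14.3.1.1.2.1 and 14.3.1.3.1.1. Report on-drug time (first to last dose) separately from post-drug time (after last dose to last contact), with time censored at the first event or the end of the window.
- **SAP 6.8.1 and the footnote to Table 14.3.0.1:** correct the formula to last dose minus first dose plus 1 before it is used for person-time.
- **SAP 8:** name the by-period TEAE tables of Protocol 8.8.1 as dropped and say why, or restore them with the number at risk at the start of each period.

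The cost is a little more programming. First-dose, last-dose, last-contact and event start dates are already in the planned listings. The rate is easiest to interpret when the hazard is roughly constant. Where it is not, the by-period tables are the better display.

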# 6.8.3 Clinical Laboratory Evaluation

By-subject listings of all laboratory data, as well as abnormal laboratory results, will be presented. Clinically significant laboratory results will be recorded as an AE.

# **6.8.4** Other Observations Related to Safety

# **6.8.4.1 Electrocardiogram Measurements**

Data will be provided in a by-subject listing.

# 6.8.4.2 Vital Signs

Data will be provided in a by-subject listing.

# 6.8.4.3 Physical Exams

Clinically significant physical exam findings will be recorded by the sites within medical history or adverse events and otherwise not summarized. Data will be provided in a by-subject listing.

#### **6.8.4.4 Menstrual Diaries**

Data will be provided in a by-subject listing.

# 6.8.4.5 Hospital Anxiety and Depression Scale (HADS)

Data will be provided in a by-subject listing.

# 6.8.4.6 Epworth Sleepiness Scale (ESS)

Data will be provided in a by-subject listing.

# 7. DETERMINATION OF SAMPLE SIZE

No formal sample size calculations were performed. Up to 700 adult subjects with pruritus associated with PN, AD, or psoriasis will be enrolled in this study.

# 8. CHANGES IN THE PLANNED ANALYSES

No graphs of laboratory values over time will be created.

Planned analyses have been updated to facilitate an abbreviated clinical study report.

# 9. INDEX OF PLANNED END-OF-TEXT TABLES AND FIGURES

Table 14.0.1.1: Summar	ry of Subject Completion/Discontinuation (Enrolled Subjects)	14
Table 14.0.2.1: Summar	ry of Subjects Excluded from Analyses (Enrolled Subjects)	15
Table 14.1.1.1: Summar	ry of Subject Demographics (Safety Population)	16
Table 14.3.0.1: Summar	ry of Extent of Exposure (Safety Population)	18
Table 14.3.1.1.1: Ove	rall Summary of Treatment-Emergent Adverse Events (TEAEs) (Sa Population)	_
Table 14.3.1.1.2.1: Sum	nmary of Subjects Reporting Treatment-Emergent Adverse Events (TEAEs) by MedDRA System Organ Class and Preferred Term (Sepulation)	Safety 20
Table 14.3.1.1.3.1: Sum	nmary of Treatment-Emergent Adverse Events (TEAEs) Leading to Discontinuation of Study Drug (Safety Population)	21
Table 14.3.1.1.4.1: Sum	nmary of Subjects Reporting Treatment-Emergent Adverse Events (TEAEs) by Severity (Safety Population)	22
Table 14.3.1.1.5.1: Sum	nmary of Subjects Reporting Treatment-Emergent Adverse Events (TEAEs) by Relationship to Study Drug (Safety Population)	23
Table 14.3.1.3.1.1: Sum	Events (TEAEs) by MedDRA System Organ Class and Preferred (Safety Population)	Term 24
Table 14.3.1.3.2.1: Sum	nmary of Subjects Reporting Serious Treatment-Emergent Adverse Events (TEAEs) by Severity (Safety Population)	25
Table 14.3.1.3.3.1: Sum	nmary of Subjects Reporting Serious Treatment-Emergent Adverse Events (TEAEs) by Relationship to Study Drug (Safety Population	n)26

Statistical Analysis Plan for Menlo Therapeutics Inc. Protocol Number: MTI-107

Table 14.0.1.1: Summary of Subject Completion/Discontinuation (Enrolled Subjects)

	Serlopitant 5 mg
	(N=xxx)
Completed Treatment	
Yes	xx ( xx.x%)
No	xx ( xx.x%)
Reason for Discontinuation from Treatment	
Adverse Event	xx (xx.x%)
Lack of Efficacy	xx ( xx.x%)
Pregnancy	xx ( xx.x%)
Investigator Decision	xx ( xx.x%)
Withdrawal by Subject from Treatment	xx ( xx.x%)
Protocol Deviation	xx ( xx.x%)
Sponsor Decision	xx ( xx.x%)
Other	xx ( xx.x%)
Completed Follow-up	
Yes	xx ( xx.x%)
No	xx ( xx.x%)
Reason for Discontinuation from Follow-up	
Withdrawal by Subject from Study	xx ( xx.x%)
Lost to Follow-up	$xx(x^0/x)$
Other	XX (XX.X%)

Table 14.0.2.1: Summary of Subjects Excluded from Analyses (Enrolled Subjects)

	Serlopitant 5 mg (N=xxx)
Safety Population	(14-AAA)
Number of Subjects Included	xx ( xx.x%)
Number of Subjects Excluded	XX (XX,X%)
Reason for Exclusion	
No Evidence of Subject Dosing	XX (XX,X%)
No Post-Baseline Assessment/TEAE	XX (XX,X%)

Table 14.1.1.1: Summary of Subject Demographics (Safety Population)
(Page 1 of 2)

	Serlopitant 5 mg
	(N=xxx)
Age (years)	
n	XXX
Mean	XX.X
SD	XX.XX
Median	XX.X
Min. to Max.	xx to xx
Sex	
n	XXX
Male	xx ( xx.x%)
Female	xx ( xx.x%)
Ethnicity	
n	XXX
Hispanic or Latino	xx ( xx.x%)
Not Hispanic or Latino	xx ( xx.x%)
Race	
n	XXX
American Indian or Alaska Native	xx ( xx.x%)
Asian	$\mathbf{x}\mathbf{x}  (\mathbf{x}\mathbf{x}.\mathbf{x}\%)$
Black or African American	XX (XX.X%)
Native Hawaiian or Other Pacific Islander	XX (XX.X%)
White	XX (XX,X'')
Multiple/Other	$\mathbf{x}\mathbf{x}  (\mathbf{x}\mathbf{x}.\mathbf{x}\%)$
Transpio Onio	AA ( AA.A./0)

Table 14.1.1.1: Summary of Subject Demographics (Safety Population)
(Page 2 of 2)

	Serlopitant 5 mg (N=xxx)
Height (cm)	(IV AAA)
N	XXX
Mean	XX.X
SD	XX.XX
Median	XX.X
Min. to Max.	xx to xx
Weight (kg)	
n	XXX
Mean	XX.X
SD	XX.XX
Median	XX.X
Min. to Max.	xx to xx

Table 14.3.0.1: Summary of Extent of Exposure (Safety Population)

	Serlopitant 5 mg (N=xxx)
otal Number of Tablets Used	XXX
n	XXX
Mean	XX.X
SD	XX.XX
Median	XX.X
Min. to Max.	xx to xx
otal Number of Days of Exposure	XXX
n	XXX
Mean	XX.X
SD	XX.XX
Median	XX.X
Min. to Max.	xx to xx
Subjects with 6-Month Exposure a	xx ( xx.x%)
Subjects with 1-Year Exposure a	xx ( xx.x%)

<sup>a Subjects considered having 6-Month exposure if date of first dose – date of last dose + 1 is greater than or equal to 182 days.

Subjects considered having 1-Year exposure if date of first dose – date of last dose + 1 is greater than or equal to 358 days, considering the allowable -7 day window for the Week 52 visit.

Table 14.3.1.1.1: Overall Summary of Treatment-Emergent Adverse Events (TEAEs) (Safety Population)

	Serlopitant 5 mg
	(N=xxx)
Subjects with any TEAE	XX ( XX.X%)
Number of TEAEs	XXX
Subjects with any Related TEAE	xx ( xx.x%)
Number of Related TEAEs	XXX
Subjects with any Serious TEAE	xx ( xx.x%)
Number of Serious TEAEs	XXX
Subjects with any Related Serious TEAE	xx ( xx.x%)
Number of Related Serious TEAEs	XXX
Subjects who Died	xx ( xx.x%)
Subjects who Discontinued Study Drug Due to TEAE	xx ( xx.x%)
Maximum Severity by Subject	
Grade 5	$XX \left( XX.X^{0}/_{0} \right)$
Grade 4	xx (xx.x%)
Grade 3	xx ( xx.x%)
Grade 2	xx ( xx.x%)
Grade 1	xx ( xx.x%)
Maximum Relationship by Subject	
Likely Related	xx ( xx.x%)
Likely Unrelated	xx ( xx.x%)

Table 14.3.1.1.2.1: Summary of Subjects Reporting Treatment-Emergent Adverse Events (TEAEs) by MedDRA System Organ Class and Preferred Term (Safety Population)

(Page 1 of xx)

System Organ Class a Preferred Term	Serlopitant 5 mg (N=xxx)
Total	xx ( xx.x%)
System Organ Class Preferred Term Preferred Term Preferred Term Preferred Term Preferred Term	xx ( xx.x%) xx ( xx.x%) xx ( xx.x%) xx ( xx.x%) xx ( xx.x%)
System Organ Class Preferred Term Preferred Term Preferred Term Preferred Term Preferred Term	xx ( xx.x%) xx ( xx.x%) xx ( xx.x%) xx ( xx.x%) xx ( xx.x%)

<sup>a Counts reflect numbers of subjects reporting one or more TEAEs that map to MedDRA. At each level of summarization (System Organ Class or Preferred Term) subjects are counted once.

MedDRA Version 21.1.

Table 14.3.1.1.3.1: Summary of Treatment-Emergent Adverse Events (TEAEs) Leading to Discontinuation of Study Drug (Safety Population)

(Page 1 of xx)

System Organ Class a Preferred Term	Serlopitant 5 mg (N=xxx)
Total	xx ( xx.x%)
System Organ Class Preferred Term Preferred Term Preferred Term Preferred Term Preferred Term	xx ( xx.x%) xx ( xx.x%) xx ( xx.x%) xx ( xx.x%) xx ( xx.x%)
System Organ Class Preferred Term Preferred Term Preferred Term Preferred Term Preferred Term	xx ( xx.x%) xx ( xx.x%) xx ( xx.x%) xx ( xx.x%) xx ( xx.x%)

<sup>a Counts reflect numbers of subjects reporting one or more TEAEs that map to MedDRA. At each level of summarization (System Organ Class or Preferred Term) subjects are counted once.

MedDRA Version 21.1.

Table 14.3.1.1.4.1: Summary of Subjects Reporting Treatment-Emergent Adverse Events (TEAEs) by Severity (Safety Population)
(Page 1 of xx)

System Organ Class a Preferred Term	Serlopitant 5 mg (N=xxx)
Total	
Grade 5	xx (xx.x%)
Grade 4	xx (xx.x%)
Grade 3	xx (xx.x%)
Grade 2	xx (xx.x%)
Grade 1	xx ( xx.x%)
System Organ Class	
Grade 5	xx (xx.x%)
Grade 4	xx (xx.x%)
Grade 3	xx (xx.x%)
Grade 2	xx (xx.x%)
Grade 1	xx ( xx.x%)
Preferred Term	
Grade 5	xx ( xx.x%)
Grade 4	xx (xx.x%)
Grade 3	xx (xx.x%)
Grade 2	xx ( xx.x%)
Grade 1	xx ( xx.x%)

<sup>a Counts reflect numbers of subjects reporting one or more TEAEs that map to MedDRA. At each level of summarization (System Organ Class or Preferred Term) subjects are counted once under the greatest reported severity.

MedDRA Version 21.1.

Grade 1=Mild; Grade 2=Moderate; Grade 3=Severe; Grade 4=Life Threatening; Grade 5=Death.

Table 14.3.1.1.5.1: Summary of Subjects Reporting Treatment-Emergent Adverse Events (TEAEs) by Relationship to Study Drug
(Safety Population)
(Page 1 of xx)

System Organ Class a Preferred Term	Serlopitant 5 mg (N=xxx)
Total Likely Related Likely Unrelated	xx ( xx.x%) xx ( xx.x%)
System Organ Class Likely Related Likely Unrelated	xx ( xx.x%) xx ( xx.x%)
Preferred Term Likely Related Likely Unrelated	xx ( xx.x%) xx ( xx.x%)

<sup>a Counts reflect numbers of subjects reporting one or more TEAEs that map to MedDRA. At each level of summarization (System Organ Class or Preferred Term) subjects are counted once under the greatest reported relationship.

MedDRA Version 21.1.

# Table 14.3.1.3.1.1: Summary of Subjects Reporting Serious Treatment-Emergent Adverse Events (TEAEs) by MedDRA System Organ Class and Preferred Term (Safety Population) (Page 1 of xx)

System Organ Class a Preferred Term	Serlopitant 5 mg (N=xxx)
Total	xx ( xx.x%)
System Organ Class Preferred Term Preferred Term Preferred Term Preferred Term Preferred Term	xx ( xx.x%) xx ( xx.x%) xx ( xx.x%) xx ( xx.x%) xx ( xx.x%)
System Organ Class Preferred Term Preferred Term Preferred Term Preferred Term Preferred Term	xx ( xx.x%) xx ( xx.x%) xx ( xx.x%) xx ( xx.x%) xx ( xx.x%)

<sup>a Counts reflect numbers of subjects reporting one or more TEAEs that map to MedDRA. At each level of summarization (System Organ Class or Preferred Term) subjects are counted once.

Note: TEAEs are AEs with an onset date after first dose of study drug.

MedDRA Version 21.1.

Table 14.3.1.3.2.1: Summary of Subjects Reporting Serious Treatment-Emergent Adverse Events (TEAEs) by Severity (Safety Population)

(Page 1 of xx)

System Organ Class a Preferred Term	Serlopitant 5 mg (N=xxx)
Total	
Grade 5	xx ( xx.x%)
Grade 4	xx ( xx.x%)
Grade 3	xx ( xx.x%)
Grade 2	xx ( xx.x%)
Grade 1	xx ( xx.x%)
System Organ Class	
Grade 5	xx ( xx.x%)
Grade 4	xx ( xx.x%)
Grade 3	xx ( xx.x%)
Grade 2	xx ( xx.x%)
Grade 1	xx ( xx.x%)
Preferred Term	
Grade 5	xx ( xx.x%)
Grade 4	xx ( xx.x%)
Grade 3	xx ( xx,x%)
Grade 2	xx ( xx.x%)
Grade 1	xx ( xx.x%)

<sup>a Counts reflect numbers of subjects reporting one or more TEAEs that map to MedDRA. At each level of summarization (System Organ Class or Preferred Term) subjects are counted once under the greatest reported severity.

MedDRA Version 21.1.

Grade 1=Mild; Grade 2=Moderate; Grade 3=Severe; Grade 4=Life Threatening; Grade 5=Death.

Table 14.3.1.3.3.1: Summary of Subjects Reporting Serious Treatment-Emergent Adverse Events (TEAEs) by Relationship to Study Drug (Safety Population)

(Page 1 of xx)

System Organ Class a Preferred Term	Serlopitant 5 mg (N=xxx)
Total Likely Related Likely Unrelated	xx ( xx.x%) xx ( xx.x%)
System Organ Class Likely Related Likely Unrelated	xx ( xx.x%) xx ( xx.x%)
Preferred Term Likely Related Likely Unrelated	xx ( xx.x%) xx ( xx.x%)

<sup>a Counts reflect numbers of subjects reporting one or more TEAEs that map to MedDRA. At each level of summarization (System Organ Class or Preferred Term) subjects are counted once under the greatest reported relationship.

MedDRA Version 21.1.

